3.0 ELIGIBILITY

Patients and Partners: A total of 198 dyads will be recruited from the community.

Drinkers and their family partners must give informed consent; agree to complete interviews at baseline, 4, 8, and 12 months; and not have a mental or physical condition that limits smartphone use. Drinkers must be age 18 or older and meet criteria for risky drinking (for men, >14 standard drinks in a week or >4 in a day; for women, >7 in a week or >3 in a day),76 or meet criteria for AUD (any severity) defined by DSM-5 and have had at least 1 drink in the past 3 months .77 Partner must be a committed romantic partner, spouse, or family member (e.g. sibling, parent, grandparent, adult child age 21 or older).

Exclusion criteria: current (last 6 months) evidence of unstabilized serious mental illness (active psychosis, delusions, hallucinations, active manic phase). We will also exclude dyads if either partner reports serious interpersonal violence in the past year, because of potential safety risk owing to access to a partner's smartphone or computer.

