Verbal consent will be documented on the recruitment form and in REDCap and a copy of the IRB-approved consent form will be mailed to participants for their records. All study data outside of REDCap will be stored in a locked cabinet at the Center for Health Enhancement Systems Studies at the UW.

Baseline interviews will be conducted with the drinker and partner individually over the phone.

Once dyads complete the pretest, the UW team will send phones and train drinkers and partners on the appropriate technology. Dyads will be informed that they will stay in the study if they do not miss two surveys in a row. If the drinker or partner declines, the dyad will be excluded. We will document reasons for refusals and monitor whether refusal rates differ by sex, race/ethnicity, and age. We will also note race/ethnicity and whether partners are of the opposite or same sex.

Recruitment sources. Many couples participating in our R34 PartnerCHESS study were recruited not from AUD/SUD treatment agencies but from advertisements in Craigslist and an email blast sent to faculty and staff at the University of Wisconsin–Madison; this indicates there is a large segment of people not in treatment who want and need help. Ultimately, our approach will be to recruit and serve dyads from addiction treatment agencies, hospitals that identify individuals with AUD, and the wider world where individuals may not have access to treatment or avoid it because of stigma. This will be a nationwide recruitment using platforms such as email marketing, targeted over-the-air advertising delivered through streaming platforms (e.g. Roku, Amazon Fire TV), local broadcast television, Craigslist, Facebook, and an email blast sent to faculty and staff at the University of Wisconsin. to increase awareness of opportunities to get help. We will also purchase advertising in newspapers that traditionally reach African American populations.

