Study design and outcomes. We will conduct a 24-month randomized trial (*N*=198 dyads, 66 in each arm, to yield approximately 180 dyads at 8-month analysis) in which assessment and intervention will all occur remotely. Dyads comprising one person who drinks at risky levels or has AUD (any severity) and one family partner (any family member) will be recruited and randomly assigned to 8 months of either: 1) smartphone control (both drinker and partner receive smartphones with numbers for AA, NA, Al-Anon, ACOA and crisis hot lines); 2) ACHESS-C (drinker receives a phone with ACHESS-C; partner receives a phone with numbers for Al-Anon, ACOA, and crisis hot lines); or 3) FamCHESS-C (drinker and partner receive a phone with FamCHESS-C). In all conditions, both members of the dyad complete baseline assessment plus follow up assessments at 4, 8, and 12 months (i.e. 8-month active app/phone use phase plus follow-up 4 months later).

[figure not shown]
Primary outcomes: 1) drinker % heavy drinking days, 2) dyad quality of life.

Secondary outcomes: 3) dyad relationship satisfaction, 4) dyad psychological/physical conflict, 5) drinker no heavy drinking days, 6) drinker % days alcohol/drug use, 7) dyad COVID vaccination rates, 8) drinker alcohol- and drug-related problems.

Exploratory outcomes: 9) partner % days alcohol/drug use, 10) dyad crisis healthcare use (ER, 30-day hospital readmits), 11) dyad satisfaction with technology.

Rationale for our primary outcomes: Quality of life captures the physical and socioemotional impacts of COVID and alcohol and comorbid drug use for drinkers and partners. Reductions in alcohol and comorbid drug use are the primary means by which we hope to improve quality of life.

Hypothesis 1: Outcomes will be more favorable in FamCHESS-C relative to ACHESS-C, and both will be more favorable relative to smartphone control.

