6.0 MEASUREMENT OF EFFECT

Variables reflect the conceptual model (see Figure 3, above) and study aims. Measures chosen have good psychometric properties with similar populations. Where possible, we used PhenX and PROMIS measures (e.g. PROMIS 29.2) so that results are comparable to other studies.⁸⁵ Our primary outcome is percent days of heavy drinking, but given 2015 FDA draft guidelines we also include number of patients with *no* heavy drinking days per period as a secondary outcome.⁸⁶ Table 2 lists our measures, number of questions, and sources, with references to validation studies where relevant. In the R34, we collected much of the same data we propose to collect in the RCT. Survey completion time averaged about 90 minutes.

Table 2: Proposed Measures, Scales, and Sources for Study Outcomes and Other	
Variables	

MEASURE	WHO	SOURCE	REFERENCE	# QUEST	TIME (MONTH)
		Primary Outcomes			
% days heavy drinking	Drinker	Timeline Follow Back ⁸⁷	Johnston et al. ⁸⁸	7	0, 4 , 8, 12
Quality of life	Dyad	PROMIS 29.2	Hamilton et al.85	29	0, 4, 8, 12
		Secondary Outcomes			
Relationship satisfaction	Dyad	OQ-45.2 ⁸⁹	Beckstead et al.89	45	0, 4 , 8, 12
Physical/psychological conflict	Dyad	Rev. Conflict Tactics	Straus et al.90	20	0, 4 , 8, 12
No heavy drinking days	Drinker	Timeline Follow Back ⁸⁷	Johnston et al. ⁸⁸	7	0, 4 , 8, 12
% days alcohol or drug use	Drinker	Timeline Follow Back ⁸⁷	Johnston et al. ⁸⁸	7	12
COVID vaccination completion	Dyad			1	0, 4 , 8, 12
Drinking/drug problems	Drinker	Clinical evaluation guide	Spitzer et al.91	5	0, 4 , 8, 12
	Ē	Exploratory outcomes			
Crisis healthcare use (ER, 30 day readmits)	Dyad	Treatment Services Reviews	McCollister & French ⁹²	3	0, 4 , 8, 12
% days alcohol or drug use	Partner	TLFB last 60 day	Collins et al. ⁸⁷	11	0, 4 , 8, 12
Satisfaction with technology	Dyad	Tech Accept Model93	Szajna ⁹⁴	26	4, 8, 12
		Mediators			
Competence	Dyad	CCQ / # of skills used	Schroder & Ollis ⁹⁵	11	0, 4 , 8, 12
Relatedness	Dyad	Revised Important People	Zwiak et al.96	14	0, 4 , 8, 12
Motivation	Dyad	Brief Self Control Scale	Tangney et al.97	13	0, 4 , 8, 12
Reductions over 8 months % days alcohol or drug use	Drinker	Timeline Follow Back ⁸⁷	Johnston et al. ⁸⁸	7	0, 4 , 8
For ACHESS-C vs. FamCHESS-C: use of app	Dyad	Smartphone data	N/A	0	0, 4 , 8, 12
		Moderators			
Sex	Drinker			1	0
Concurrent treatment services	Drinker	TSR	McLellan et al.98	10	0, 4 , 8, 12
Severity baseline alcohol	Drinker	Smartphone data	N/A	0	0, 4 , 8, 12

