8.0 STATISTICAL CONSIDERATIONS

Data Analysis Plan. The analysis will: 1) explore differences among the three arms over the 8-month active intervention phase and then the 4-month follow-up phase of the RCT; 2) explore the conceptual model (see Figure 3) that considers the relations between the primary and secondary outcomes, and drinker and partner mediators, moderators, and covariates; and 3) examine how the dyad's demographic characteristics (e.g. young drinker and older partner) affect intensity and length of ACHESS-C and FamCHESS-C use and SDT mediators of relatedness, motivation, and competence on study outcomes.

Assumptions and randomization effect. We will report descriptive statistics for all demographic and clinical variables in both arms to ensure that randomization produced comparable groups; if not, variables with significant differences will be included as covariates in a sensitivity analysis. Sensitivity analyses (with and without covariate adjustment) will determine the robustness of covariate-related error control. All outcome variables will be examined using standard summary statistics, visualizations, and tests for normality and homoscedasticity. Data will be transformed for continuous outcomes that do not meet the assumptions of a normally distributed outcome.

Effects of study arm on primary and secondary outcomes (Aim 2). Linear mixed effects models (LMEM)—which account for dependence among successive observations on the same drinker and can address incomplete data—will be used to examine effects of study arm (FamCHESS-C vs. ACHESS-C vs. control, a between-subjects factor) on drinker outcomes over time. We will conduct specific treatment X time contrasts both between and within groups to test time-based effects. For binary, count, and other non-normal data, generalized linear mixed effects models will be used.

Mediation of effects of study arm on primary outcomes (Aim 3). Structural equation modeling (SEM) will explore the effects of mediation on the relation between study arms and our two primary outcomes. We anticipate that the impact of study arm on drinker heavy drinking days and dyad quality of life will be mediated by SDT (competence, relatedness, and motivation) and by drinker's interim change in percent alcohol and drug use days. SEMs involving app use will be run separately for only the ACHESS-C and FamCHESS-C arms.

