Qualitative Analyses (Aim 4). Transcripts of qualitative interviews concerning perceived difficulties and benefits of app use will be examined using Braun and Clarke's¹⁰² six-phase procedure for thematic analysis: 1) familiarization with data, 2) generation of initial codes, 3) identifying instances of themes, 4) review of themes, 5) defining and naming themes, 6) production of findings. To improve consistency and accuracy, coders will work separately using NVivo software; findings will be compared and discussed until consensus is reached.

Interim Analyses and Stopping Plan. The interim analyses are solely to check whether the stopping plan needs to be implemented. They will not be reported as tests of our hypotheses and thus will not inflate Type 1 error. We will engage in the following practices: 1) We will report any fatalities as they occur, as required by the university IRB. 2) Our statistician will conduct interim analyses at months 18 and 27 after the start of the study (9 and 18 months after recruiting begins), examining our primary outcome of substance use days in the two arms. She will share the results with UW's independent Data Safety and Monitoring Board but not with the Pls unless instructed to do so by the Board. Because all of our prior research has been designated low-risk by

the IRB, we anticipate the same designation in this case. Barring exceptional disparities in outcomes between conditions, we do not anticipate stopping the trial. As an *a priori* rule, we believe we should stop if our primary outcome of functional health shows a T-score difference greater than 6 (averaged across components of the PROMIS-29). A T-score of 6 is at the very upper end of the clinically meaningful differences for PROMIS-29 components (e.g. physical function, pain, fatigue).^{22,30} We have no reason to anticipate such an occurrence. We will follow Data Safety Monitoring Board guidance on this matter.

Missing Data. In previous RCTs, we completed about 85% of interviews through 12 months and kept missing data on core interview items to about 2%. We expect these rates in this study. We will identify missing data patterns and use pattern-mixture modeling to test the sensitivity of our analysis to missing data assumptions.¹⁰³⁻¹⁰⁶ We will conduct other sensitivity analyses after imputing missing data with a range of plausible values based on assumptions for the missing data (e.g. best-case, worst-case; with and without multiple imputation).¹⁰⁷⁻¹⁰⁹

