10.0 DATA SECURITY AND PRIVACY MONITORING PLAN

Data and Safety Monitoring Committee

The Center uses the Data Monitoring Committee (DMC) located in the University of Wisconsin's Institute for Clinical and Translational Research (ICTR). The ICTR DMC will provide services to ensure appropriate measures are in place to promote subject safety, research integrity and compliance with federal regulations and local policies. The DMC members will review protocol-specific reports created by statisticians using data pulled from the Research Electronic Data

Capture (REDCap) data management tool. These standard reports will include an overview of study objectives, a review of actual and projected accrual rates, an evaluation of patient demographics for balance of randomization, and a summary of the number and seriousness of adverse events. An interim analysis of study results may be performed and source documents may be reviewed to allow the board to independently judge whether the overall integrity and conduct of the protocol remain acceptable based on data provided and reported by the Principal Investigators. The board will make recommendations to the Principal Investigator that could include actions of continuation, modification, suspension, or termination.

In providing oversight for the conduct of this study, the ICTR DMC will meet annually during the 3-year study. Additional meetings may be scheduled as determined by the DMC or as requested by the PIs.

We will record events that are deemed to be 'possibly, probably, or definitely' related to the study intervention, and communicate to NIAAA, DMC and UW IRB in accordance with the following guideline.

What Event is Reported	When is Event Reported	By Whom is Event Reported	To Whom is Event Reported	
Fatal or life- threatening unexpected, suspected	Within 7 calendar days of initial	Investigator	Internal IRBs NHLBI and/or DMC	
serious adverse reactions	receipt of information	Sponsor or designee	FDA (if IND study)	
Non-fatal, non-life- threatening unexpected, suspected	Within 15 calendar days of initial receipt of information	Investigator	Internal IRBs/ Institutional Officials NHLBI and/or DMC	
serious adverse reactions		Sponsor or designee	FDA All participating investigators	
Unanticipated adverse	Within 10 working days of	Investigator	Internal IRBs NHLBI and/or DMC	
device effects	investigator first learning of effect	Sponsor or designee	FDA (if IDE study)	

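### Exploratory outcome 10 counts hospital stays only as 30-day readmissions, so in this community-recruited sample a first or single unplanned admission is not counted as an admission

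*Combined protocol and SAP*

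**What the plan says.** Outcome 10 appears in three places. Section 2.0 (Aim 2) names it without components. Section 5.0 (Aim 2, exploratory outcomes) gives it as "dyad crisis healthcare use (ER, 30-day hospital readmits"). Table 2 in section 6.0 lists it as "Crisis healthcare use (ER, 30 day readmits"), measured in both dyad members with three Treatment Services Review questions at months 0, 4, 8 and 12. Neither of the last two places marks its components as examples, and neither says which stay starts the 30-day window.

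On the population, section 3.0 states that "A total of 198 dyads will be recruited from the community", and a hospital stay is not an entry criterion for drinker or partner. Section 4.0 (Recruitment sources) adds that the approach will be to "recruit and serve dyads from addiction treatment agencies, hospitals that identify individuals with AUD", and also to recruit from the wider public. It gives no shares by source.

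**The concern.** A 30-day readmission measure suits people who have just left hospital. Here most participants need have no prior stay, so the inpatient part of the outcome cannot register their first unplanned admission, nor a second one that begins more than 30 days after discharge. A first hospital stay for COVID, a harm that section 1.0 stresses, would not be counted as an admission either.

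What is at stake is how well an exploratory outcome describes what it names. The more severe end of crisis healthcare use is either merged with ER visits that end in discharge home or left out of the outcome.

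**Working it through.** **Applying the definition as written**, to a participant with no recent discharge:
- One unplanned admission contributes 0 to the inpatient part.
- A second admission within 30 days of that discharge contributes 1.
- A second admission more than 30 days after it contributes 0.
- An ER visit on the way to any of these counts under the ER part, where it looks the same as a visit without admission.

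**Looking for another count of admissions.**
- No other listed outcome counts them.
- The Table 2 moderator "Concurrent treatment services" (Treatment Services Review, 10 questions) is for drinkers only and its content is not given. It could not supply partner admissions for a dyad outcome.
- Section 10.0 promises the monitoring committee "a summary of the number and seriousness of adverse events", but the events recorded are those judged at least possibly related to the intervention. That is not a count of all unplanned admissions.
- Section 5.0 mentions clinic-record data in a confidentiality paragraph, but the records list in section 9.0 does not include such data.

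**Size.** The plan states no figure for this outcome, so there is none to reproduce.

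Inputs from the plan: 66 dyads per arm, 12 months of follow-up, and from section 8.0 (Missing Data) "we completed about 85% of interviews through 12 months" in previous trials, a rate expected again here.

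Assumptions, not from the plan:
- 5 to 15 admissions per 100 person-years, 60 to 80% of them unplanned. That is 5 × 0.60 = 3 to 15 × 0.80 = 12 unplanned per 100 person-years; middle value 6.
- 10 to 25% of admissions are 30-day readmissions; middle value 15%.
- 70 to 90% of unplanned admissions enter through the ER.

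Reported person-years per arm = 66 × 2 × 1 × 0.85 = 112.2.

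| | Low | Middle | High |
|---|---|---|---|
| Unplanned admissions per arm | 112.2 × 0.03 = 3.37 | 112.2 × 0.06 = 6.73 | 112.2 × 0.12 = 13.46 |
| Counted as readmissions | 3.37 × 0.10 = 0.34 | 6.73 × 0.15 = 1.01 | 13.46 × 0.25 = 3.37 |
| Chance an arm has no readmission (Poisson) | exp(−0.34) = 71% | exp(−1.01) = 36% | exp(−3.37) = 3% |

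**Share of unplanned admissions not counted as admissions.**
- If nobody enrols soon after a discharge: 1 − 0.25 = 75% to 1 − 0.10 = 90%.
- Of all unplanned admissions in that case, 0.70 × 0.75 = 53% to 0.90 × 0.90 = 81% appear only as an ER visit.
- Another 0.10 × 0.75 = 8% to 0.30 × 0.90 = 27% leave no trace in outcome 10.
- If 20% of drinkers enrol just after discharge and 30% of those are readmitted, the extra counted events are 66 × 0.20 × 0.30 × 0.85 = 3.37 per arm. At the lowest admission rate and a 25% readmission share, the uncounted share falls to 3.37 × 0.75 / (3.37 + 3.37) = 37.5%.

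**What broader counting buys.** Take two independent Poisson counts with means L and L/2 and an exact conditional test at two-sided 5%. Power to detect a halving is 3%, 11% and 25% (low, middle, high) with all unplanned admissions, and at most 3% with readmissions only. For precision, equal counts of 7 v 7 give an exact 95% interval for the rate ratio of 0.30 to 3.3; 1 v 1 gives 0.01 to 78.

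**The case against.** The strongest case on the other side is that this reads a short label as if it were an operational definition. Table 2 lists three items for two named components, and a survey can hardly identify a 30-day readmission without asking about an earlier stay. The questionnaire may therefore already ask about admissions, and the drinkers' 10-question row may do so too. ER visits are themselves crisis use, and on the assumptions above most unplanned admissions would at least leave an ER visit. All the rates are assumed, with one rate applied to drinkers and partners alike. The outcome is tenth of eleven, exploratory, and underpowered under any definition.

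Much of this stands. It limits the point to the definition and keeps it minor. It does not remove the point: both places that give content say readmissions only, and following them scores a single admission as zero on the inpatient part whatever the survey collects.

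Three stronger readings are tempting and not supported:
- That admission data will be missing. The items are not reproduced, so this cannot be shown.
- That the inpatient part will be empty, or that most admissions are certain to be missed. Readmission counts are sparse but not necessarily zero, and because section 4.0 allows hospital recruitment without stating shares, the uncounted share could be as low as 38%.
- That a broader definition would make the arm comparison informative. Power stays at 25% or less.

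**Conclusion.** The point holds as one about definition. Outcome 10 restricts its inpatient part to 30-day readmissions in a sample that needs no prior stay, so a first or single unplanned admission is not counted as an admission unless it falls within 30 days of an earlier discharge. Under the assumed rates that means about 0.3 to 3 events counted per arm, against about 3 to 13 unplanned admissions reported. The reading of the definition rests on the text; these sizes rest wholly on assumptions. The benefit of changing it is a description by arm that matches the outcome's name. The primary and secondary results and the stopping rule are not affected. It is a cheap improvement that the sponsor could make, not a flaw that threatens the trial.

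**What to change.** Define the inpatient component of outcome 10 as any unplanned overnight hospital admission since the last survey. Report ER visits separately and keep 30-day readmissions as a descriptive subset. Give counts and a simple rate comparison with a confidence interval by arm, not a hypothesis test. The models in section 8.0 ("For binary, count, and other non-normal data, generalized linear mixed effects models will be used") are set out there under a heading for primary and secondary outcomes and may not converge with 3 to 13 events per arm, so the simple comparison is the safer choice.

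The cost is a revised definition and at most one reworded survey item to separate planned stays such as elective surgery or childbirth, with some self-report misclassification. Aim 1 already provides for survey refinements. If the existing items prove to record unplanned admissions, only the definition needs to change.

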6.0 MEASUREMENT OF EFFECT

Variables reflect the conceptual model (see Figure 3, above) and study aims. Measures chosen have good psychometric properties with similar populations. Where possible, we used PhenX and PROMIS measures (e.g. PROMIS 29.2) so that results are comparable to other studies.⁸⁵ Our primary outcome is percent days of heavy drinking, but given 2015 FDA draft guidelines we also include number of patients with *no* heavy drinking days per period as a secondary outcome.⁸⁶ Table 2 lists our measures, number of questions, and sources, with references to validation studies where relevant. In the R34, we collected much of the same data we propose to collect in the RCT. Survey completion time averaged about 90 minutes.

Table 2: Proposed Measures, Scales, and Sources for Study Outcomes and Other	
Variables	

MEASURE	WHO	SOURCE	REFERENCE	# QUEST	TIME (MONTH)
		Primary Outcomes			
% days heavy drinking	Drinker	Timeline Follow Back ⁸⁷	Johnston et al. ⁸⁸	7	0, 4 , 8, 12
Quality of life	Dyad	PROMIS 29.2	Hamilton et al.85	29	0, 4, 8, 12
		Secondary Outcomes			
Relationship satisfaction	Dyad	OQ-45.2 ⁸⁹	Beckstead et al.89	45	0, 4 , 8, 12
Physical/psychological conflict	Dyad	Rev. Conflict Tactics	Straus et al.90	20	0, 4 , 8, 12
No heavy drinking days	Drinker	Timeline Follow Back ⁸⁷	Johnston et al. ⁸⁸	7	0, 4 , 8, 12
% days alcohol or drug use	Drinker	Timeline Follow Back ⁸⁷	Johnston et al. ⁸⁸	7	12
COVID vaccination completion	Dyad			1	0, 4 , 8, 12
Drinking/drug problems	Drinker	Clinical evaluation guide	Spitzer et al.91	5	0, 4 , 8, 12
	Ē	Exploratory outcomes			
Crisis healthcare use (ER, 30 day readmits)	Dyad	Treatment Services Reviews	McCollister & French ⁹²	3	0, 4 , 8, 12
% days alcohol or drug use	Partner	TLFB last 60 day	Collins et al. ⁸⁷	11	0, 4 , 8, 12
Satisfaction with technology	Dyad	Tech Accept Model93	Szajna ⁹⁴	26	4, 8, 12
		Mediators			
Competence	Dyad	CCQ / # of skills used	Schroder & Ollis ⁹⁵	11	0, 4 , 8, 12
Relatedness	Dyad	Revised Important People	Zwiak et al.96	14	0, 4 , 8, 12
Motivation	Dyad	Brief Self Control Scale	Tangney et al.97	13	0, 4 , 8, 12
Reductions over 8 months % days alcohol or drug use	Drinker	Timeline Follow Back ⁸⁷	Johnston et al. ⁸⁸	7	0, 4 , 8
For ACHESS-C vs. FamCHESS-C: use of app	Dyad	Smartphone data	N/A	0	0, 4 , 8, 12
		Moderators			
Sex	Drinker			1	0
Concurrent treatment services	Drinker	TSR	McLellan et al.98	10	0, 4 , 8, 12
Severity baseline alcohol	Drinker	Smartphone data	N/A	0	0, 4 , 8, 12
Baseline relationship	Dyad	Smartphone data	N/A	0	0, 4 , 8, 12
satisfaction	-			_	
MEASURE	WHO	SOURCE	REFERENCE	# QUEST	TIME (MONTH)
Covariates					
Age	Drinker & partner			1	0
Education	Drinker & partner			1	0
Race/ethnicity	Drinker & partner			2	0

Psychiatric treatment history	Drinker & partner	Question (PhenX tier 1)	Collins et al.87	1	0, 4, 8, 12
COVID acute & residual symptoms	Drinker & partner	Acute and Persistent Symptoms: COVID-19	Carfi et al.99	17	0, 4, 8, 12
Sex	Partner			1	0

